9.1.5. Sample Size Estimation

A sample size of 55 subjects per treatment group will have 80% power to detect a treatment difference of 0.43 units with a common standard deviation 0.80 in iCFS score, and a treatment difference of 13.75 units with a common standard deviation 25.5 in eye dryness score at Visit 6/Day 84 using a t-test with a 0.05 two-sided significance level.

9.1.6. Level of Significance

Nominal P-values will be reported at the 5% level of significance if applicable.

9.1.7. Procedure for Accounting for Missing, Unused, or Spurious Data

Any missing, unused, or spurious data will be noted in the final clinical study report. The data will be analyzed as reported. The last observation carried forward approach will be used to analyze incomplete datasets.

9.1.8. Procedure for Reporting Deviations from the Statistical Plan

Any deviations from the statistical analysis plan will be described and a justification given in the final clinical study report.

10. SUPPORTING DOCUMENTATION AND OPERATIONAL CONSIDERATIONS

10.1. Direct Access to Source Data/documents

The Investigator will permit trial-related monitoring, audits, IRB review, and regulatory inspection(s) by providing direct access to source data and documents (such as tests performed as a requirement for participation in the study and other medical records required to confirm information contained in the eCRF such as medical history) to the monitor or appropriate designee.

10.2. Quality Control

The progress of the study will be monitored by on-site, written, e-mail, and telephone communications between personnel at the study center and the Sponsor (or designated monitor). The Investigator will allow VivaVision Biotech, Inc. monitors or designees to inspect all eCRFs; subject records (source documents); signed informed consent forms; HIPAA authorizations; records of IP receipt, storage, and disposition; and regulatory files related to the study.

10.3. Good Clinical Practice (GCP)

This clinical trial will be conducted in compliance with the protocol, International Council on Harmonisation (ICH) guidelines, Good Clinical Practice (GCP) guidelines, and other applicable regulatory requirements.

10.4. Collection of Data

Source documentation for data collected in this study will be maintained at the investigative site. In cases where no source will be used (e.g., dosing diary), it will be noted in the Investigator files. The CRF will be electronic (eCRF) and data will be entered from source documentation into the eCRF. After study completion, an archival copy [e.g., Portable Document Format (PDF)] of the eCRF data will be retained by the site.

10.5. Ethics

10.5.1. Institutional Review Board

This protocol and the informed consent form must be approved by an appropriately constituted and qualified IRB and the approvals made available to the Sponsor or designee prior to the start of enrollment into the study. Materials used to recruit subjects will be approved by the appropriate IRB and the approvals made available to the Sponsor or designee prior to their use. In addition, the Investigator's Brochure should be submitted to the IRB. Written IRB approval must adequately identify the protocol and ICF. Copies of all approved materials, all correspondence with the IRB, and written approval from the IRB must be made available to the Sponsor (or designated monitor).

Any modification of study procedures or amendments to the protocol must be approved by the IRB prior to implementation. In the event that a modification or amendment is considered by the Investigator to be immediately necessary to ensure subject safety, the Investigator will promptly notify his or her IRB and the Sponsor.

Investigators will report all SAEs reported at their site to their IRB, as appropriate.

10.5.2. Informed Consent Requirements

Written informed consent will be obtained from each participant prior to any study-related procedures being performed (prior to or upon Visit 1/Screening). A copy of the signed and dated informed consent document will be given to each subject. The original signed and dated informed consent document must be maintained in the study files at the investigative site and be available for Sponsor or designee review.

Each informed consent will contain Investigator contact information with a telephone number the subject or the subject's authorized representative can call 24 hours a day if they have medical concerns.

10.6. Data Handling and Recordkeeping

All procedures for the handling and analysis of data will be conducted using GCP and will meet ICH guidelines and FDA regulations for the handling and analysis of data for clinical trials.

10.6.1. Data Quality Control and Reporting

After data have been entered into the study database, a system of computerized data validation checks will be implemented and applied to the database. Query reports pertaining to data omissions and discrepancies will be forwarded to the clinical Investigator and monitor(s) for resolution. The study database will be updated in accordance with the resolved query reports. All changes to the study database will be documented.

10.6.2. Records Retention

The study center will retain all records related to the study in accordance with local and ICH GCP guidelines.

10.6.3. Publication Policy

The Institution and Investigators participating in this trial shall have no right to publish or present the results of this study without the prior written consent of the Sponsor.

12. APPENDICES

APPENDIX 1: SCHEDULE OF EVENTS

	VISIT 1	VISIT 2	VISIT 3	VISIT 4	VISIT 5	VISIT 6
	SCREENING	RANDOMIZATION	TREATMENT VISIT	TREATMENT VISIT	TREATMENT VISIT	FINAL TREATMENT VISIT
	DAY - 14 (+/- 1 DAY)	DAY 1 (+/- 2 DAYS)	DAY 14 (+/- 2 DAYS)	DAY 28 (+/- 2 DAYS)	DAY 56 (+/- 2 DAYS)	DAY 84 (+/- 2 DAYS)
INFORMED CONSENT AND MEDICAL HISTORY	X					
INCLUSION/EXCLUSION CRITERIA ^D	X	X				
CONCOMITANT MEDICATION QUERY	X	X	X	X	X	X
ASSESS PRIOR ARTIFICIAL TEAR USE	X					
CLINICAL SAFETY LABORATORIES AND HEMATOLOGY	X					X
ADVERSE EVENT QUERY		X	X	X	X	X
COLLECT STUDY DRUG		X ^B		X ^C	X ^C	X ^C
SUBJECT-REPORTED 2-SYMPOTM ASSESSMENT (EYE DRYNESS AND EYE DISCOMFORT; VAS)	X	X	X	X	X	X
SANDE	X	X	X	X	X	X
PREGNANCY TEST ^A	X					X
BCVA	X	X	X	X	X	X
	VISIT 1	VISIT 2	VISIT 3	VISIT 4	VISIT 5	VISIT 6
	SCREENING	RANDOMIZATION	TREATMENT VISIT	TREATMENT VISIT	TREATMENT VISIT	FINAL TREATMENT VISIT

	VISIT 1	VISIT 2	VISIT 3	VISIT 4	VISIT 5	VISIT 6
	SCREENING	RANDOMIZATION	TREATMENT VISIT	TREATMENT VISIT	TREATMENT VISIT	FINAL TREATMENT VISIT
	DAY - 14 (+/-1 DAY)	DAY 1 (+/-2 DAYS)	DAY 14 (+/-2 DAYS)	DAY 28 (+/-2 DAYS)	DAY 56 (+/-2 DAYS)	DAY 84 (+/-2 DAYS)
	DAY - 14 (+/-1 DAY)	DAY 1 (+/-2 DAYS)	DAY 14 (+/-2 DAYS)	DAY 28 (+/-2 DAYS)	DAY 56 (+/-2 DAYS)	DAY 84 (+/-2 DAYS)
BIOMICROSCOPY/EXTERNAL EXAM	EYE	X	X	X	X	X
CFS STAINING		X	X	X	X	X
SCHIRMER (WITHOUT ANESTHESIA)		X	X	X	X	X
IOP		X	X	X	X	X
DILATED OPHTHALMOSCOPY		X				X
IP ADMINISTRATION IN CLINIC		X^b	X^c			X^c
DROP COMFORT ASSESSMENT		X	X			X
DISPENSE IP		X^b	X^c		X^c	X^c
DISPENSE DOSING AND SYMPTOM DIARY (AS NEEDED)		X	X		X	X
COLLECT DAILY DIARY			X	X	X	X
EXIT STUDY						X

^aWomen of childbearing potential only; ^bRun-In Drug; ^cDouble-Masked IP; ^dSubjects must replicate the following findings in the same eye at Visits 1 and 2 in order to be considered for further study eligibility: 1) Inferior CFS score ≥ 2 (0 – 4 scale; using 0.5 increments) and (2) STT without anesthesia ≥ 1 and ≤ 7 mm, at Visits 1 and 2. If both eyes meet the

two criteria above, the eye with the greater inferior CFS be selected as the study eye. If both eyes have an equal inferior CFS score at Visit 2, the eye with the lowest STT value at Visit 2 will be designated as the study eye. If both eyes have equal score in inferior CFS and equal STT scores at Visit 2, the right eye (OD) will be selected as the study eye.

APPENDIX 2: DROP COMFORT/TOLERABILITY ASSESSMENT

You will be asked to rate the comfort of the drop for both eyes as one score at 1-minute and 5-minutes post dose at Visits 1, 2 and 6.

[figure not shown]
Drop Comfort/Tolerability

COMFORT/TOLERABILITY OF INVESTIGATIONAL PRODUCT		
Overall Comfort of Investigational Product: 0=Comfortable and 10=Uncomfortable		
0	5	10
<hr/>		

APPENDIX 3: INVESTIGATOR-RATED ASSESSMENT OF SIGNS OF CONJUNCTIVAL HYPEREMIA

Investigator-Rated Assessment of Bulbar conjunctival hyperemia

Investigators will rate overall bulbar conjunctival hyperemia using the Cornea and Contact Lens Research Unit (CCLRU) Grading Scale.

0 = None

1 = Very Slight

2 = Slight

3 = Moderate

4 = Severe

APPENDIX 4: ETDRS BEST CORRECTED VISUAL ACUITY

Visual Acuity (VA) testing should precede any examination requiring contact with the eye or instillation of study dyes, as is detailed in the order of assessments for each Visit in Section 6.1. Logarithm of the Minimal Angle of Resolution (LogMAR) visual acuity must be assessed using an ETDRS or modified ETDRS chart. Visual acuity testing should be performed with best correction using subject's own corrective lenses (spectacles only) or pinhole refraction.

An ETDRS or modified ETDRS chart may be used. If a Lighthouse chart is used (24.5" by 25"; either reflectance or retro-illuminated), the subject must view the chart from a distance of exactly 4 meters (13.1 feet). If smaller reproductions (18" by 18", e.g., Prevent Blindness) are used, the subject viewing distance should be exactly 10 feet. Reflectance wall charts should be frontally illuminated (60 watt bulb or a well-lit room).

The subject should be positioned according to the elevation of the chart (either seated or standing) so that the chart is at a comfortable viewing angle. The right eye should be tested first. The subject should attempt to read each letter, line-by-line, left to right, beginning with line 1 at the top of the chart. The subject should be told that the chart has letters only, no numbers. If the subject reads a number, he or she should be reminded that the chart contains no numbers, and the examiner should then request a letter instead of the number. The subject should be asked to read slowly, about 1 letter per second, to achieve the best identification of each letter. He/she is not to proceed to the next letter until he/she has given a definite response. If the subject changes a response before he has read aloud the next letter, then the change must be accepted.

Maximum effort should be made to identify each letter on the chart; the subject should be encouraged to guess. When it becomes evident that no further meaningful readings can be made, the examiner should stop the test. The number of letters missed or read incorrectly should be noted.

In order to provide standardized and well-controlled assessments of visual acuity during the study, the same lighting conditions must be used consistently throughout the study.

Calculations: LogMAR VA = Baseline value + (n X 0.02)

where:

the baseline value is the LogMAR number of the last line read (at least 1 letter read correctly in this line), and “n” is the total number of letters missed up to and including the last line read, and “0.02” is the value for each letter.

APPENDIX 5: SLIT-LAMP BIOMICROSCOPY

The biomicroscopy exam should be performed with the slit lamp using a beam width and intensity that provide optimal evaluation of the anterior segment.

This procedure will be performed in the same manner for all subjects observed at the Investigator's site. The site will record all ABNORMAL findings in the source document and the Investigator will evaluate the ABNORMAL findings as Non-Clinically Significant (NCS) or Clinically Significant (CS). CS and NCS ABNORMAL findings will be recorded in the source documentation. However, only ABNORMAL CS descriptions will be captured in the eCRF.

Lashes

- 0 = Normal
- 1 = Abnormal

Eyelid

Edema

- 0 = Normal, no swelling of the lid tissue
- 1 = Abnormal

Skin

- 0 = Normal, including but not limited to thinning, pigment changes, dermatitis
- 1 = Abnormal

Conjunctiva

Edema

- 0 = Normal, no swelling of the conjunctiva
- 1 = Abnormal

Cornea

Infiltrates

- 0 = Absent
- 1 = Present

Endothelial Changes

- 0 = Normal, None
- 1 = Abnormal, pigment, keratoprecipitates, guttata

Edema

- 0 = Normal, None, transparent and clear
- 1 = Abnormal

Anterior Chamber

Cells

- 0 = Normal, No cells seen
- 1 = Abnormal (+ to +++ cells)

Flare

- 0 = Normal, No Tyndall effect
- 1 = Abnormal, Tyndall beam in the anterior chamber

Lens Pathology

- 0 = Normal, no opacity in the lens
- 1 = Abnormal, existing opacity in the lens; aphakic or pseudophakic eyes or other abnormal findings

Sclera

- 0 = Normal
- 1 = Abnormal

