8.1.2. Procedures for AE Reporting by the Investigator

AEs will be monitored throughout the study and will be recorded on the eCRF with the date and time of onset, date and time of resolution, severity, seriousness, causality (relationship to use of IP), treatment required, and the outcome.

To elicit AEs, simple questions with minimal suggestions or implications should be used as the initial questions at all evaluation points during the trial. For example:

- How have you felt since your last assessment?
- Have you had any health problems since your last assessment?

The severity of each AE should be categorized as mild, moderate, or severe.

The causality of use of IP in relation to the AE will be assessed by the Principal Investigator after careful medical consideration and categorized as unrelated, unlikely, possible, probable, or definite.

If an AE occurs, the Investigator will institute support and/or treat as deemed appropriate.

If a non-SAE is unresolved at the time of the last day of the study, an effort will be made to follow up until the AE is resolved or stabilized, the subject is lost to follow-up, or there is some other resolution of the event. The Investigator should make every attempt to follow SAEs to resolution.

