4.8.1. Safety Assessments

The following safety assessments will be summarized at each visit if applicable using descriptive statistics for SAF population by treatment group and overall. Assessments will be presented for study eye and non-study eye separately.

- Slit-Lamp biomicroscopy and external eye exam
 - For each anterior segment such as lashes, eyelid, conjunctiva, cornea, anterior chamber, lens pathology and sclera, the summary tabulations of the frequency and percentage for evaluation category such as normal, abnormal CS (clinically significant) and abnormal NCS (non-clinically significant) will be presented. The worsening (from normal to abnormal CS\NCS) change from baseline will be flagged in the data listing.
- Dilated Ophthalmoscopy
 - The evaluation of normal and abnormal for each eye in retina and optic nerve exam will be tabulated by using the frequency and percentage. The cup-to-disc ratio by visits and absolute change from baseline at Visit 6 (Day 84) will be presented using descriptive statistics.
- Intraocular Pressure (IOP) measurement (mmHg)
 - Absolute change from baseline at post-baseline visits will be summarized using descriptive statistics. The frequency and percentage of subjects with increase in $IOP \geq 10$ mmHg from baseline at each post-baseline visits and any visit will be summarized and presented in the data listing as well.
- Best Corrected Visual Acuity (BCVA)
 - LogMAR Visual Acuity (VA) score and change from baseline will be calculated and summarized using descriptive statistics. The frequency and percentage of

Statistical Analysis Plan

Sponsor:	VivaVision Biotech, Inc.		
Protocol:	VVN001-CS-201		
Document Version No.:	V3.0	Document Date:	13-JAN-2022

subjects with loss in VA ≥ 0.3 LogMAR (3 lines) from baseline at each post-baseline visits and any visit will be summarized and presented in the data listing.

- Conjunctival Hyperemia Evaluation
 - Overall bulbar conjunctival hyperemia grading scale: none, very slightly, slight, moderate and severe will be tabulated by using the frequency and percentage for each eye. The worsening (from low to high grading scale) change from baseline will be flagged in the data listing.
- Drop Comfort/Tolerability Assessment
 - The one scored for both eyes on VAS range from 0 to 10 at 1-minute and 5-minute post dose and absolute change from baseline at Visit 6 (Day 84) will be summarized using descriptive statistics.

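### Appendix 5 places dermatitis, pigment change and thinning under the Normal code for eyelid skin, so an exam scored as printed counts lid-skin pathology as normal

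*Protocol*

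**What the plan says.** Protocol section 8.1 sends both slit-lamp biomicroscopy and the external eye exam to Appendix 5, which scores each item 0 or 1. For eyelid skin, code 0 reads "0 = Normal, including but not limited to thinning, pigment changes, dermatitis" and code 1 is a bare Abnormal.

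Two other items show the usual layout. The adjacent eyelid-edema item defines code 0 as "0 = Normal, no swelling of the lid tissue". The corneal-endothelium item puts its pathology under the other code: "1 = Abnormal, pigment, keratoprecipitates, guttata".

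The code decides what happens next. Appendix 5 says "The site will record all ABNORMAL findings in the source document"; the investigator then rates each one as clinically significant (CS) or not (NCS), and "only ABNORMAL CS descriptions will be captured in the eCRF".

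SAP section 4.8.1 tabulates the results: "For each anterior segment such as lashes, eyelid, conjunctiva, cornea, anterior chamber, lens pathology and sclera", in categories "such as normal, abnormal CS (clinically significant) and abnormal NCS (non-clinically significant) will be presented". A change from normal to either abnormal category is flagged in the listing.

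Adverse events follow a separate route. Protocol section 8.1.2 says "AEs will be monitored throughout the study and will be recorded on the eCRF".

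**The concern.** The eyelid-skin line gives three pathological findings as examples of normal skin. An examiner who follows it scores new dermatitis as 0, and a finding scored 0 never enters the steps reserved for abnormal findings. An examiner who assumes the line is a slip scores the same lid as 1. Nothing in either document says which to do.

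The item matters because slit-lamp and external examination is a named safety endpoint (protocol section 2.2.1; SAP section 2.4.1), and the SAP makes safety and tolerability its primary objective (section 1.2.1). The drops go into both eyes twice daily for about 84 days, and the exam is scheduled at all six visits. This is the only item in the safety examination that scores lid skin: conjunctival hyperemia (Appendix 3) and drop comfort (Appendix 2) do not.

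**Working it through.** No arithmetic in the plan bears on this point, so the check is a comparison of the items and a trace of the code.

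**Step 1. The eleven items of Appendix 5, paraphrased.**

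| Item | What code 0 describes | What code 1 describes |
|---|---|---|
| Lashes | nothing beyond Normal | nothing beyond Abnormal |
| Eyelid edema | absence of swelling | nothing beyond Abnormal |
| **Eyelid skin** | **three pathological findings** | **nothing beyond Abnormal** |
| Conjunctival edema | absence of swelling | nothing beyond Abnormal |
| Corneal infiltrates | absent | present |
| Endothelial changes | none | named pathology |
| Corneal edema | none, clear cornea | nothing beyond Abnormal |
| Anterior chamber cells | none seen | cells, over a range of grades |
| Anterior chamber flare | no Tyndall effect | Tyndall beam |
| Lens | no opacity | opacity and other named findings |
| Sclera | nothing beyond Normal | nothing beyond Abnormal |

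Four items name their pathology under code 1 (endothelium, cells, flare, lens). Three define code 0 as absence and leave code 1 bare (the edema items). One is absent/present, two carry no descriptors, and one is eyelid skin: 4 + 3 + 1 + 2 + 1 = 11. Eyelid skin alone puts pathology under code 0.

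**Step 2. One subject traced through the rules.** Take a lid with normal skin at baseline, dermatitis on treatment and no lid edema at either visit.

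| Stage | Scored as printed | Examples moved to code 1 |
|---|---|---|
| Code, baseline to visit | 0 to 0 | 0 to 1 |
| Required source record of an abnormal finding | no | yes |
| CS/NCS rating | none | CS or NCS |
| Description in the eCRF | none | only if CS |
| Eyelid abnormal count, SAP 4.8.1 | not counted | counted |
| Worsening flag in the listing | none | flagged |

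The scale does not mention cause, so the trace is the same for dermatitis due to the drops and dermatitis due to anything else.

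**Step 3. What this does to a comparison of arms.** Let p1 and p0 be the true proportions with new lid-skin change in an active arm and in vehicle. Let s be the share of such changes that are coded 1. Treatment is masked, so assume s is the same in both arms and that no normal lid is coded 1. Then

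observed difference = s × p1 − s × p0 = s × (p1 − p0).

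If every site codes literally, s = 0 and the item shows no difference whatever the truth. If every site codes by intent, s = 1 and nothing is lost. A mixture falls between. The error therefore shrinks a real difference on this item; it does not create one. The documents give neither s nor p, so the formula sets the direction, not a count.

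**The case against.** The strongest reply is that this is a typographical slip whose intent is plain. The three edema items share the skin item's layout, with a descriptor on code 0 and a bare code 1, so a dropped negation explains the line as well as a misplaced list does. On either account dermatitis is meant to be abnormal, and an investigator making an ordinary normal/abnormal judgement may well code it so. The source worksheet and eCRF labels that sites work from are not among the documents. This stands as a limit on how often the wording would mislead. It does not remove the defect: the printed scoring rule is the reverse of the apparent intent, and neither document corrects it.

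The second reply is that safety capture does not depend on this code. Protocol section 8.1.1 defines an adverse event as any untoward occurrence, with no requirement for symptoms, and the simple questions in section 8.1.2 are described as initial ones. Adverse events are queried at Visits 2 to 6, and treatment-emergent events are the primary safety analysis (section 9.1.4). The slit-lamp table is descriptive. All of this stands, and it confines the loss to the exam dataset.

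Three stronger readings are tempting, and the documents do not support them:

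- **That the trial would miss drop-related lid dermatitis.** Adverse-event reporting remains open for anything the investigator sees, and the scale says nothing about cause.
- **That sites will score the same lid in opposite directions.** The text supports could, not will.
- **That a particular number of cases would be lost.** No incidence of lid-skin change, and no share of sites reading literally, appears in either document.

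**Conclusion.** The point holds: the eyelid-skin item is wrong as printed. Followed literally, it scores lid-skin pathology of any cause as normal and keeps it out of the CS/NCS rating, the eyelid abnormal counts and the worsening flag. Followed by intent, it does not, so coding could differ between the approximately 10 centers.

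The size is modest. One item of one descriptive safety table and its listing is exposed. Adverse-event data, efficacy endpoints, hypothesis tests and sample size are unaffected. For findings that are not clinically significant, no eCRF description is lost, because none was due.

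The conclusion rests on two assumptions: that sites score from the wording in Appendix 5, and that no worksheet or completion guide outside these documents already corrects it. The expectation that the error shrinks a difference between arms without favoring either also assumes that masking held and that the mix of literal and intent-based coding was similar across arms.

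**What to change.** Amend the eyelid-skin item so that code 0 is Normal without examples and code 1 is Abnormal with thinning, pigment change and dermatitis as non-exhaustive examples. Bring the source worksheet and the eCRF completion guidance into line.

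For visits already completed, ask each site to document, before database lock and unmasking, which convention it used, and state any inconsistency alongside the eyelid table in the study report. Checking code-0 entries against source notes is a weak substitute: Appendix 5 requires only abnormal findings to be recorded in source, so a site that coded literally may have nothing to find.

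The cost is a one-line change to the appendix and worksheet and one question to each site. The small downside is that some chronic lid-skin changes will be recorded as abnormal NCS at baseline.
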